15.2 Appendix B - APACHE II Score

APACHE II Score:

- For each variable used in the APACHE II Score, the value from the previous 24 hours yielding the most points should be used
- Since it is not possible to assess the Glasgow Coma Scale (GCS) in patients who are sedated and paralyzed, by convention it is regarded as normal, unless it is known that there was a brain injury prior to sedation, as in the case of head injury (but not confusion associated with tiredness, hypoxia, etc.). This will result in a GCS of 15 and a neurologic score of 0 (zero).
- Chronic Health Evaluation

If any of these conditions are marked "Y", assign points based on the patient's condition at the time of ICU admission (or in the 24-hour period prior to screening) - See Section C on last page.

Organ insufficiency or immuno-compromised state must have been evident prior to this hospital admission and conform to the following criteria.

LIVER : Biopsy-proven cirrhosis and documented portal hypertension. or episodes of past upper GI bleeding attributed to portal hypertension, or prior episodes of hepatic failure/encephalopathy/coma.								
CARDIOVASCULAR: New York Heart Association Class IV.								
RESPIRATORY: Chronic restrictive, obstructive, or vascular disease resulting in severe exercise Y restriction, (i.e., unable to climb stairs or perform household duties); or documented chronic hypoxia, hypercapnia, secondary polycythemia, severe pulmonary hypertension (>40 mm Hg), or respirator dependency.								
RENAL: Receiving chronic hemo- or peritoneal dialysis.	Y	N						
IMMUNO-COMPROMISED:								
(1) The patient has received therapy that suppresses resistance to infection, eg immuno- suppressive agents, chemotherapy, radiation, long term low dose steroids, 10 mg/day prednisone for >1 month prior to hospitalization) or recent high dose steroids (> 15 mg/kg/day of hydrocortisone or >3 mg/kg/day of methylprednisolone for >5 days).	Y	Ν						
(2) The patient has a disease that is sufficiently advanced to suppress resistance to infection	Y	N						

(2) The patient has a disease that is sufficiently advanced to suppress resistance to infection, Y N eg leukemia, lymphoma, AIDS, documented diffuse metastatic cancer.

Phys	siologic Variable		HIGH ABN (Check one	ORMAL I	RANGE variable and	write the s	everity sco	LOV re in the co	W ABNOR	MAL RAN right.	GE
			Note: use	the worst p	ossible scor	e for all va	riables, exc	ept for the	GCS score.) 5	Severity Score
	Severity Points	+4	+3	+2	+1	0	+1	+2	+3	+4	
1	Temperature – rectal (°C)										
	-	≥41°	39-40.9°		38.5°-38.9°	36°-38,4°	34°-35.9°	32°-33.9°	30°-31.9°	≤29.9°	
2	Mean Arterial Pressume (mmHg)										
		≥160	130-159	110-129		70-109		50-69		≤49	
3	Heart Rate (Ventricular Response)										
		≥180	140-179	110-139		70-109		55-69	40-54	≤39	
4	Resp. Rate (non-ventilated or ventilated)										
		≥50	35-49		25-34	12-24	10-11	6-9		≤5	
	Oxygenation:										
5	a. $FIO_2 \ge 0.5$ record A·aDO ₂ *	≥500	350-499	200-349		<200					
-	b. $FIO_2 < 0.5$ record only PaO_2										
						PaO ₂ >70	PaO ₂ 61-70		PaO ₂ 55-60	PaO ₂ <55	
6	Arterial pH										
		≥7.7	7.6-7.69		7.5-7.59	7.33-7.49		7.25-7.32	7.15-7.24	<7.15	
7	Serum Sodium (mmol/L)										
		≥180	160-179	155-159	150-154	130-149		120-129	111-119	≤110	
8	Serum Potassium (mmol/L)										
		≥7	6-6.9		5.5-5.9	3.5-5.4	3-3.4	2.5-2.9		<2.5	
9	Serum Creatinine (µmol/L)										
	(double point score for acute renal failure)	≥309.4	176.8-309.3	132-177		53-133		<53			
10	Hematocrit (%)										
		≥60		50-59.9	46-49.9	30-45.9		20-29.9		<20	
11	White Blood Count (total/mm ³)										
	(in 1000s)	≥40		20-39.9	15-19.9	3-14.9		1-2.9		<1	
12	Glasgow Coma Score (GCS)						(Note:	The best GCS	S used for the 1	st 24 hours)	(15 - GCS Total)
	Score=15 minus actual GCS	Eye	Verbal	Motor	GCS Total	(= Eye + Ver	bal + Motor)				
	A=Total ACUTE PHYSIOLO	GY SCO	RE (APS): T	(APS): Total severity points indicated for Variables 1-12 in the column to the right.							
	Serum HCO ₃ (venous-mmol/L)										
	(Use in place of variable 5 if no ABGs)	≥52	41-51.9		32-40.9	22-31.9		18-21.9	15-17.9	<15	1
* * *	DO [/E'O /712) /D-OO /0.0)1 D-O										-

 $A \cdot aDO_2 = [(FiO_2 (713) - (PaCO_2/0.8))] - PaO_2$

Glasgo	w Coma Scale	Age Points = B		Chronic health Points = C	Apache-II Score Sum of A + B + C
Circle appropriate resp Eyes open: 4 = spontaneously	onse verbal - nonintubated: 5 = oriented and Controverses	Age ≤ 44	Points 0	If the patient has a history of severe organ systems insufficiency or is immuno compromised, assign points as follows	APS points A =
2 = to painful stimuli 1 = no response	 4 = disoriented and talks 3 = inappropriate words 2 = incomprehensible sounds 1 = non response 	45 5 55 6 65 7 ≥7	4 2 4 3 4 5 5 6	 5 points for nonoperative or emergency postopera tive patients 2 points for elective postoperative patients Otherwise zero (0) points 	Age points B =
Motor response 6 = to verbal command 5 = localizes to pain 4 = withdraws to pain	 verbal - intubated: 5 = seems able to talk 3 = questionable ability to talk 1 = generally unresponsive 	Age	Points =		Chronic health points C =
3 = decorticate 2 = decerebrate				Chronic Health Points =	Total Apache II =

Final Protocol ATB-202 version 4.0 23 Aug 2018

15.3 Appendix C - modified SOFA

Value	0	1	2	3	4
Respiratory PaO ₂ /FiO ₂ ¹	>400	≤400	≤300	≤200 with respiratory support	≤100 with respiratory support
Coagulation Platelets	>150	≤150	≤100	≤50	≤20
Cardiovascular ²	No hypo- tension	MAP <70	Dopa ≤5 PE <100	Dopa > 5 Epi ≤ 0.1 NE ≤ 0.1 PE 100- 300	Dopa>15 Epi>0.1 NE>0.1 PE>300 VP>0.01
Neuro GCS	15	13-14	10-12	6-9	<6
Serum Creatinine OR Urine Output	<1.2	1.2-1.9	2.0-3.4	3.5-4.9 <500cc/ day	≥5.0 <200cc/ day

1. For patients on supplemental oxygen via nasal cannula, nasopharyngeal catheter or mask and for converting SpO2 values to PaO2 use the attached oxygen conversion tables.

2. Doses of dopamine (Dopa), epinephrine (Epi), norepinephrine (NE) are in micrograms/kg/min; phenylephrine (PE) is micrograms/min; vasopressin (VP) is U/min. Vasopressors must have been administered for at least one hour.

Oxygen Conversion tables

Estimating Pa02 from a given Sp02

SpO2 (%)	PaO2 (mmHg)
80	44
81	45
82	46
83	47
84	49
85	50
86	52
87	53
88	55
89	57
90	60
91	62
92	65
93	69
94	73
95	79
96	86
97	96
98	112
99	145

Estimating Fi02

Method	O2 flow	Estimated FiO2 (%)
Nasal cannula	1	24
	2	27
	3	30
	4	33
	5	36
	6	40
Nasopharyngeal catheter	4	40
	5	50
	6	60
Face mask	5	40
	6-7	50
	7-8	60
Face mask with reservoir	6	60
	7	70
	8	80
	9	90
	10	95

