4.3.7 Visit 7 (Day 14 [±1 day])

- Collect data on operative procedures
- Weight

- Collection of AEs/SAEs, including secondary infections (based on CDC definitions for healthcare associated infections)
- Collect data on additional amputations
- Collect data on acute renal replacement therapy
- Collect data on plasma or platelet transfusion
- Selected concomitant medications (e.g. vasopressors, antimicrobials)
- Safety laboratory tests (Chemistry, Hematology)
- Collect blood for serum for storage (immunogenicity testing)
- **P**E
- Vital signs
- CRP
- Critical care parameters (dates and times of assisted ventilation, vasopressor use, ICU /hospital stay)
- Systemic response: collect data for mSOFA parameters
 - All efforts should be made to obtain the actual measurements of SOFA parameters at these visits-may use SpO2 value (and record FiO2) if arterial blood gas is not clinically indicated.
 - In case a patient is discharged from hospital prior to these days SOFA parameters should be obtained on the same day of discharge.
- Assess lesion status (healing/progression/significant change in appearance) if accessible for visible assessment at time of debridement or routine dressing change
- Record Survival

All efforts should be made to collect these data, but in case parameters cannot be collected, phone follow-up will be performed, and information that could be collected over the phone will apply.

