15. APPENDICES

15.1 Appendix A - Study visits and procedures

Visit	1	2	3	4	5	6	7	8	9	10
	Screening	Day	Day	Day	Day 7	Day 10	Day	Day 21 ±1	Day 29 +2	3
		1	2	3	±1	±1	14	days	days	months
					day	day	±1			$\pm 5 \text{ days}$
							days			
Informed Consent	Х									
Demographics	Х									
Medical history	Х									
Lesion history	Х									
Concomitant Medications ^a	Х	Х	Х	X	Х	Х	Х	Х	Х	
Weight & Height ^b	Х				Х		X		Х	
Urine output ^c										
Vital Signs ^d	X	X	X	X	Х	X	Х	Х	X	
Physical Examination (PE)	X				Х		Х			
Interim PE (symptom-driven)		Х		X		Х				
Baseline Signs & Symptoms ^e	X									

^a See Section 5.2 for instruction on level of detailed information required for recording concomitant medications

^b Height will be taken only at screening

^c Urine output is required for Days 1-7 (while the patient is in the ICU and has a Foley catheter in place) to assess for development or resolution of acute kidney injury.

^d Systolic & Diastolic blood pressure, Heart rate, Respiration rate, Temperature; (first set of vitals on that visit day)

^e Adverse events reported from ICF signature to AB103 administration

Final Protocol ATB-202 version 4.0 23 Aug 2018

Visit	1	2	3	4	5	6	7	8	9	10
	Screening	Day 1	Day 2	Day 3	Day 7 ±1 day	Day 10 ±1 day	Day 14 ±1 days	Day 21 ±1 days	Day 29 +2 days	3 months ±5 days
12-Lead ECG	X	X ^f								
Blood Chemistry ^g	Х	X ^h	Xh	Xh	Х	Xh	Х	Xh	X ⁱ	Xh
C-reactive protein	Х						Х			
Blood Hematology ^j	X	Х	Х	Х	Х	Х	Х	Х	Х	
Pregnancy test ^k (if applicable)	Х									
Blood for leukocyte transcriptome (RNA expression) profile ¹	X	Х	Х	X ^l	Х					
Urine and Plasma for Storage ^m	X		Х		X					
Arterial blood gases (if applicable)	X	Х	Х	Х	X	Х	Х	Х	Х	

^f 12 lead ECG will be performed at the end of the study drug infusion, then within 4-6 hours and 12-24 hours of study drug administration, and the time of its performance should be recorded.

^g Glucose; Electrolytes - Sodium, Potassium, Calcium; Phosphorus, Chloride, Bicarbonate; Renal function tests – Urea/BUN, Creatinine; Liver function tests – Albumin, Bilirubin Total, Alanine transaminase (ALT), Aspartate transaminase (AST), Alkaline phosphatase (ALP); Protein Total. In case of abnormal results at the end of the study the results should be followed by the investigator until the abnormalities are resolved or determined as stabilized.

^h Only Creatinine. At Visit 10 (3 months), creatinine obtained only if day 29 creatinine is abnormal.

ⁱ Creatinine and Albumin only

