15.5 Appendix E - Clinical Scores

Table 7: Clinical Scores Parameters

Parameter	LRINEC	Anaya	mSOFA	APACHE II
Clinical				
Cardiovascular system (Mean Arterial Pressure)			+	+
Heart Rate		+		+
Nervous system (Glasgow Coma Score)			+	+
Oxygenation (Calculation)			+	+
			(PaO ₂ /FiO ₂)*	(Pao2 or A-a difference)
Respiratory rate				+
Temperature				+
		Т		(rectal)
Demographics				
Age		+		+
Chronic health evaluation				+
Laboratory				
Arterial pH				+
Coagulation Function (Platelets)			+	
C-Reactive Protein	+			
Renal system / Creatinine	+	+	+	+
Glucose	+			
Hemoglobin/Hematocrit	+	+		+
Sodium	+			+
Potassium				+
Total white cell count	+	+		+

*In case it is not possible to obtain arterial blood gases to determine the SOFA respiratory parameter, SpO2/FioO2 ratio can be imputed for PaO2/FiO2 ratio

Immunosuppressive Agent ^a	Upper limit dosage use	
1. Corticosteroid	> 40 mg/day of prednisone or its equivalent daily for $>$ 2 weeks.	
Equivalent Dose (mg)		
a) Prednisone	40 mg	
b) Hydrocortisone	160 mg	
c) Methylprednisolone	32 mg	
d) Dexamethasone	6 mg	
e) Cortisone	200 mg	
f) Betamethasone	4.8 mg	
2. Methotrexate (Rheumatrex, Trexall)	Excluded at any dose.	
3. Leflunomide (Arava)/Teriflunomide (Aubagio)	Acceptable if being used as monotherapy.	
4. Cyclophosphamide (Cytoxan)	Excluded at any dose.	
5. Cyclosporine A	Excluded at any dose.	
	Ophthalmic formulation (Restasis) is permitted	
6. FK506 (Tacrolimus)	Excluded at any dose	
	Topical formulation (Protopic) is permitted.	
7. Azathioprine	Excluded at any dose.	
8. Cancer Chemotherapy	Patients having received cancer chemotherapy in the previous 4 weeks are excluded.	

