2.3 Key Secondary AKI Endpoint

The same endpoint that is being currently employed in the ongoing ATB-203 study of AKI in sepsis will be evaluated as the key secondary endpoint in this study. The key secondary endpoint is *freedom from durable loss of renal function at Day 28*. Only subjects with AKI Stage 2 or Stage 3 prior to initial drug dosing will be included in this comparison. The key secondary endpoint requires:

- (i) Alive at Day 28,
- (ii) Free of dialysis at Day 28, and
- (iii) Less than a 37% loss of estimated Glomerular Filtration Rate (eGFR; measured with the Modification of Diet in Renal Disease (MDRD) formula from the patient's reference eGFR)) at Day 28.

Reference creatinine values, baseline AKI stage and percentage loss of eGFR at Day 14 and 28 will be determined through algorithmic determination (see details below). Percentage loss of eGFR determined algorithmically will be based on a comparison of eGFR at screening compared to an algorithmically determined reference creatinine value. A sensitivity analysis will utilize an independently adjudicated reference value to determine baseline eGFR.

To control type 1 error for the key secondary efficacy endpoint, superiority of Reltecimod relative to placebo in terms of freedom from durable loss of renal function at Day 28 among those presenting with Stage 2 or Stage 3 AKI will only be interpreted as a confirmatory hypothesis test if $p \le 0.01$ for the primary endpoint (NICCE) and $p \le 0.05$ for the co-primary endpoint (CCPE).

Otherwise, treatment group comparisons in terms of the key secondary efficacy (AKI) endpoint will be interpreted as a descriptive endpoint. An unadjusted chi-square test using a two-sided type 1 error of α =0.05 will be used to test superiority of Reltecimod relative to placebo for the key secondary AKI endpoint.

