4.1.4.4 Day 14 eGFR

Day 14 eGFR will be determined by converting Day 14 creatinine to Day 14 eGFR using the following formula:

Day 14 eGFR (mL/min/1.73 m²) = $175 \times (Cr Day 14)^{-1.154} \times (Age)^{-0.203} \times (0.742 if female) \times (1.212 if African American).$

Percentage loss in eGFR at Day 14 will be determined using the following formula.

Percentage loss in eGFR at Day 14 = 100% times [Screening eGFR - (Day 14 eGFR) / Screening eGFR]. If percentage loss $\ge 37\%$ then patient fails the Day 14 endpoint.

4.1.4.5 Determining AKD Stage at Day 28

Exhibit 2 will also be used to determine AKD Stage at Day 28 except that the criterion for renal replacement therapy is an ongoing need rather than initiation.

4.1.4.6 Determining AKD Stage at Day 14

Similarly, Exhibit 2 will be used to determine AKD Stage at Day 14 except that the criterion for renal replacement therapy is an ongoing need rather than initiation.

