SOFA – Sequential Organ Failure Assessment score

Can range from 0 -24

Respiratory system:

PaO ₂ / FiO ₂ (mmHg)	SOFA score
=>400	0
< 400	1
< 300	2
< 200 and mechanically ventilated	3
< 100 and mechanically ventilated	4

Nervous System:

Glasgow Coma Scale	SOFA score
15	0
13-14	1
10-12	2
6-9	3
< 6	4

Cardiovascular System

Mean Arterial Pressure (MAP) OR administration of vasopressors (mcg/Kg/minute)	SOFA score
$MAP \Rightarrow 70 \text{ mmHg}$	0
MAP < 70 mmHg	1
Dopamine <= 5 OR Dobutamine any dose	2
Dopamine > 5 <=15 OR epinephrine <=0.1 OR norepinephrine <= 0.1	3
Dopamine > 15 OR epinephrine > 0.1 OR norepinephrine > 0.1	4

MAP= (Systolic pressure + (2*Diastolic pressure))/3

Liver:

Bilirubin (mg/dl)	SOFA score
<1.2	0
1.2-1.9	1
2.0-5.9	2
6.0-11.9	3
>= 12.0	4

Coagulation:

Platelets x 10 ³ /mcl	SOFA score
=>150	0
< 150	1
< 100	2
< 50	3
< 20	4

Renal System:

Creatinine (mg/dl) (or urine output)	SOFA score
<1.2	0
1.2 - 1.9	1
2.0 - 3.4	2
3.5 - 4.9 (or < 500 ml/day)	3
>=5.0 (or < 200 ml/day)	4

Anaya score

Can range from 0 - 12

Variable on admission	Points
Heart Rate > 110 beats per minute	1
Temperature < 36.0 °C	1
Serum Creatinine > 1.5 mg/dl	1
Age > 50	3
White blood cells count > 40,000/mcl	3
Hematocrit > 50%	3

LRINEC – Laboratory Risk Indicator for Necrotizing Fasciitis

Can range from 0 - 13

	П
Variable, Units	Score
C-Reactive Protein mg/L	
< 150	0
>= 150	4
Total White Blood cells count per mm ³	
< 15	0
15 - 25	1
>25	2
Hemoglobin g/dL	
>13.5	0
11.0 – 13.5	1
< 11	2
Sodium mmol/L or meq/L	
>= 135	0
< 135	2
Creatinine µmol/L (mg/dL)	
<= 141 (1.595)	0
>141 (1.595)	2
Glucose mmol/L (mg/dL)	
<=10 (180.18)	0
>10 (180.18)	1

16 Appendix 6: Randomization Program: SAS call to R program

```
proc format;
value treatment fmt
  1 = 'Placebo'
  2 = 'Active'
run;
proc iml;
submit / R;
library(doParallel)
site hold <- seq(10, 49, by = 1)
strata hold <- c(1,2,3,4)
block 4 < -c(1,1,2,2)
block_6 <- c(1,1,1,2,2,2)
theseed = 42
set.seed(theseed)
site loop <- foreach (si = site hold, .combine=rbind) %do% {</pre>
  site num <- si
  strata loop <- foreach (s = strata hold, .combine=rbind) %do% {</pre>
    strata num <- s
    full block <- foreach (i =1:5, .combine=rbind) %do% {</pre>
      get random block <- rbinom(1, 1, 0.5)</pre>
      if (get random block == 1) {
        block <- sample(block 6, 6, replace = FALSE)
      if (get random block == 0) {
        block <- sample(block 4, 4, replace = FALSE)</pre>
      full block <- as.matrix(block)</pre>

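### The mSOFA renal score in NICCE has no rule for renal replacement therapy, so a patient still on dialysis at Day 14 can be scored as having resolved organ dysfunction

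*Protocol*

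**What the plan says.** **Scoring tables.** In Protocol 15.3 (Appendix C) the renal row is headed "Serum Creatinine OR Urine Output". Creatinine below 1.2 scores 0, 1.2–1.9 scores 1, 2.0–3.4 scores 2, 3.5–4.9 scores 3 and 5.0 or more scores 4. Urine output enters only at scores 3 and 4 (below 500 and below 200 cc/day). SAP Appendix 5 has the same cut-offs, under "Creatinine (mg/dl) (or urine output)" and in rows such as "3.5 - 4.9 (or < 500 ml/day)". Neither table has a dialysis criterion.

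**Handling rules.** SAP 5.2 and 5.10.1 cover missing organ scores and LOCF, and 5.2 also covers screening GCS inflated by ventilation or medication. Neither mentions RRT. Under Protocol 6.2.8, every mSOFA after screening is calculated retrospectively by blinded statisticians.

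**Data collected.** Protocol Appendix A, footnote c: "Urine output is required for Days 1-7 (while the patient is in the ICU and has a Foley catheter in place)". Urine output is not in the visit lists for Days 10, 14, 21 or 29. RRT is recorded: the Day 14 list (4.3.7) says "Collect data on acute renal replacement therapy", and the same item stands in the lists from screening to Day 29.

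**Use of the score.** NICCE (SAP 2.1.2) requires mSOFA of 1 or less at Day 14 and a fall of at least 3 points from baseline.

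**Dialysis elsewhere in the SAP.** RRT is Stage 3 in Exhibit 2. For AKD stage at Day 14 (4.1.4.6) "the criterion for renal replacement therapy is an ongoing need rather than initiation". The key secondary endpoint (2.3) requires "Free of dialysis at Day 28".

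**The concern.** The systemic component of NICCE is meant to show that organ dysfunction has resolved. Dialysis and hemofiltration lower serum creatinine whether or not the kidney has recovered. A score built on creatinine alone can therefore record the effect of the treatment as recovery of the organ.

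The other support-dependent rows of Appendix C do not have this gap. The cardiovascular row scores vasopressor dose, and the top two respiratory grades require respiratory support. Only the renal row has no place for organ support.

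The primary endpoint is at stake, along with everything else that uses the same score: time to resolution, the mSOFA means, the MMRM, and the survival comparison by Day 14 mSOFA in SAP 9.6. The conditional co-primary endpoint (CCPE) has no mSOFA component and is unaffected.

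**Working it through.** **1. Does any rule catch the patient?** Setting the relevant places side by side:

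- Renal row, both documents: creatinine or urine output only.
- Urine output: not scheduled after Day 7, and before that only in the ICU with a Foley catheter.
- Protocol Appendix E, to which the schedule refers for the mSOFA parameters: the only renal entry is "Renal system / Creatinine".
- SAP 5.2 and 5.10.1: no RRT rule.
- Calculation from recorded parameters by statisticians: no clinical override is described.
- Exclusions 14 and 15: these cover chronic RRT, and continuous hemofiltration for acute kidney dysfunction not due to NSTI. Patients with NSTI-related acute kidney dysfunction may be enrolled, and RRT may start after dosing.

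No rule catches the patient.

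**2. Worked case under the rules as written.**

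| | Creatinine (mg/dL) | Renal | Other organs | mSOFA |
|---|---|---|---|---|
| Screening | 5.0 or more | 4 | 0 | 4 |
| Day 14, on dialysis | 1.5 | 1 | 0 | 1 |

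The Day 14 score is 1 and the fall is 4 − 1 = 3, so both systemic components are met. If the patient is alive at Day 28 with at most 3 debridements and no later amputation, NICCE is a success. Screening creatinine of 4 or more makes this patient Stage 3 in Exhibit 2, so the patient also belongs to the AKI analyses. There, ongoing need for RRT on the same Day 14 is AKD Stage 3.

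**3. The plan's power figures.** Inputs from SAP 2.4.1: n = 145 per arm, two-sided α = 0.01 (z = 2.576), rates centred on 0.5. With d = p₁ − p₂ and p̄ the mean rate,

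power = Φ{[d − z·√(2p̄(1−p̄)/n)] / √(p₁(1−p₁)/n + p₂(1−p₂)/n)}.

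For d = 0.20 (0.60 vs 0.40): [0.20 − 2.576 × 0.05872] / 0.05754 = 0.847, so power is 80.2%, as stated. For 0.25 the result is 95.9% (stated 95.9%) and for 0.30 it is 99.6% (stated 99%). These figures are not in dispute.

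**4. Equal misclassification.** Take 0.60 vs 0.40 as scored and move the same share of each arm from success to failure. With 1% per arm, power is 80.2%; with 5% per arm, 80.6%. Power is essentially unchanged.

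**5. Unequal misclassification (assumed rates).** The documents give no rate of RRT at Day 14. For illustration, suppose 2–10% of patients are alive and on RRT at Day 14, and 20–40% of those meet every component as scored. False successes are then 0.02 × 0.20 = 0.4% to 0.10 × 0.40 = 4% of an arm, or 0.6 to 5.8 patients of 145. If all fell in the placebo arm, a true difference of 0.20 would appear as 0.196 to 0.16, with power of 78.1% down to 56%. In the other direction, with no true difference (0.40 in both arms), an excess of false successes in one arm of 1%, 2% or 3% would raise the two-sided 1% error to about 1.1%, 1.5% or 2.1%.

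**6. Sensitivity near the boundary.** Pooled chi-square, 145 per arm:

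| Successes, AB103 vs placebo | p |
|---|---|
| 82 vs 61 | 0.0136 |
| 82 vs 60 | 0.0098 |
| 84 vs 61 | 0.0069 |
| 83 vs 61 | 0.0098 |
| 87 vs 58 | 0.0007 |
| 80 vs 58 | 0.0097 |

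From 82 vs 61, reclassifying one placebo success turns a miss into p≤0.01. From 84 vs 61, reclassifying two AB103 successes gives 82 vs 61 and loses significance. At 87 vs 58, seven AB103 successes can be reclassified (80 vs 58) without losing it.

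**The case against.** **The event may be rare.** Creatinine of 2.0 or more already fails. At 1.2–1.9, one further organ point fails, for example platelets of 150 or less or GCS below 15. The 3-point fall, survival, debridement and amputation criteria must also be met. SAP 2.4.1 reports NICCE in 30.4% (21/69) of the whole retrospective cohort with mSOFA of 3 or more, so assuming 40% success among patients still on RRT is generous. This stands: the rates in step 5 are illustrations only, and the upper end is hard to credit.

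**A reader might infer a loss of power, or a bias that hides benefit in particular.** The documents support neither. The loss needs the errors to fall mainly in the placebo arm, and no passage states a hypothesis that AB103 spares patients RRT; the companion AKI trial's endpoint merely includes freedom from dialysis. The planned differences also came from earlier NICCE rates for which no RRT rule is described, so 0.20 may already be a difference as scored.

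**False trial success is buffered.** SAP 2.2 also requires p≤0.05 on the CCPE, which this issue cannot affect. This stands.

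**Urine output might still be obtained at Day 14.** Protocol 4.3.7 asks for all efforts to obtain the actual SOFA parameters, and Appendix C names urine output. But the visit list omits it, footnote c ends it at Day 7 and Appendix E lists only creatinine. Reliance on creatinine is the natural reading, though the eCRF is not available to confirm it.

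**The score follows a published SOFA structure, and the SAP cites a validation of NICCE.** True, and it is the reason to keep the as-written version as a sensitivity analysis. It does not remove the conflict with the SAP's own treatment of RRT.

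**Conclusion.** The concern holds as a defect of endpoint definition. Applied literally, the rules can count a dialysis-dependent patient as a NICCE responder while the same SAP grades that patient AKD Stage 3 on the same day. The conclusion rests on the text of both documents and on the reading that the Day 14 renal score uses creatinine.

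Its size is unknown. Equal misclassification leaves power at 80.2–80.6%, so the sample size needs no revision. What remains is the face validity of the primary endpoint, and the fact that a result close to p = 0.01 can turn on one or two patients. A clear result, such as 87 vs 58, would be robust to several.

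A reader might go further and treat this as a flaw that must be fixed before NICCE can be interpreted at all. With no documented frequency, and with the CCPE untouched, the documents do not carry that. It should be fixed, because the fix is cheap now and would not be credible after unblinding.

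**What to change.** Before unblinding, add to SAP 5.2, 5.10.1 and Appendix 5:

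- A patient with ongoing need for RRT at a post-baseline assessment gets the maximum renal score (4) in the retrospectively calculated mSOFA, whatever the creatinine, and so fails the Day 14 systemic component. Use the criterion of SAP 4.1.4.6.
- Define ongoing need, which the SAP leaves undefined, by a stated window that covers days between intermittent sessions. State how the rule applies when the Day 14 score is imputed by LOCF.
- Leave screening and baseline mSOFA, eligibility and stratification unchanged. Rescoring baseline to 4 would make the 3-point fall easier for those patients and create a second screening score.
- Report NICCE under the as-written scoring as a sensitivity analysis.

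The RRT data are already collected and have a listing (16.2.8.28), so no new data collection is needed. The costs are the work of defining the window, slightly lower NICCE rates, and a small departure from the scoring behind the planning figures.
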